#### **5.2.5.2 Unscheduled Visit**

Additional visits may be scheduled, as necessary, to ensure the safety and well-being of subjects. All additional exams should be fully documented in the subject's record and on Unscheduled Visit e-CRFs, as appropriate. Visits intended to fulfill scheduled visit requirements that fall outside the designated scheduled visit range, are not Unscheduled Visits. In these cases, the visit data will be collected and recorded in the appropriate scheduled visit e-CRF.

If a subject is seen for multiple visits during a given visit timeframe, the data from the visit that is intended to meet the protocol requirements for the scheduled visit should be captured on the visit e-CRF. Where such a determination cannot be made, the first visit within the scheduled visit interval will be used for completion of the protocol required scheduled visit e-CRF. Data from any additional visits within a scheduled visit interval will be captured on an Unscheduled Visit e-CRF.

*NOTE: All VA measurements MUST be made using a phoropter.*

- a. Indicate the reason for the Unscheduled Visit.

*NOTE: If the subject is experiencing problems, complete the entire Unscheduled Visit Form. If this visit is to dispense study materials only and the subject is not experiencing any problems refer to Section 5.2.6.*

- b. Collect the following lens information from the subject:
  - average daily wearing time
  - average hours of comfortable wear
  - total number of days of lens wear
- c. Complete the Symptoms/Complaints section within the Unscheduled Visit Form **using the Rating Scale included in initial shipment.**

- d. If the subject did not come to the visit wearing one or more study lenses, go to step e. Otherwise, evaluate the lenses (while on eye) and record the following assessments:
- distance lens VA
  - over-refraction and distance VA
  - lens wettability
  - lens deposits
  - lens centration
  - lens movement

For each eye, compare the high contrast distance lens VA to the high contrast distance lens VA obtained at the visit at which the lenses were dispensed. If the VA has decreased by 10 letters (0.2 logMAR) or more, explain.

- e. Perform a slit lamp examination (remove the lenses if the subject wore lenses to the visit and place the lenses in a lens case provided filled with *Bausch + Lomb Biotrue™ multi-purpose solution*).

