### **5.2.8 Post-Study Follow-up Visit**

If a subject requires further follow-up upon discontinuation or completion of the study, the Investigator must schedule post-study follow-up visits, as necessary.

*NOTE: All VA measurements MUST be made using a phoropter.*

- a) Remove any contact lenses the subject may be wearing. Perform a slit lamp examination (remove the lenses if the subject wore lenses to the visit). Record the results in the subject's e-CRF.
- b) Complete an ocular examination without lenses on the eyes, including spherocylindrical refraction and distance BSCVA.
- c) The Investigator is required to follow the subject until the condition no longer warrants further follow-up for study purposes. A Post-Study Follow-up Visit e-CRF must be completed for each of these visits.
- d) The following e-CRFs should be completed and submitted.
  - Post-Study Follow-up Visit

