#### Secondary Effectiveness Endpoints

- Lens performance survey (100 point scales) questions.

Study ROC2-17-014 - Protocol

- Comfort upon insertion
- Overall comfort
- Comfort at end of day

Secondary Safety Endpoints

- The proportion of subjects with any slit lamp findings grade 2 or greater at any time.

[figure not shown]
Hypotheses

The following hypotheses will be tested for each question in the take home performance questionnaire at each week.

1. The null hypothesis is that the proportion of subjects providing a response in the top three categories is equal between the treatment groups.
2. The alternative hypothesis is that the proportion of subjects providing a response in the top three categories is not equal between the treatment groups.

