#### 7.5 Study Populations

Subject eyes will be included in all summaries under the treatment that they actually received. Analyses of safety data will include all dispensed subjects. All other summaries will include all eligible, dispensed subjects.

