#### 7.6 Statistical Analysis

Primary and secondary analyses will be performed on all eligible, dispensed eyes (completed and discontinued eyes pooled) for efficacy endpoints and for all dispensed eyes (completed and discontinued eyes pooled) for safety endpoints.

Questionnaire responses to the take home questionnaire will be summarized using categorical summary statistics by treatment and week. The proportion of subjects providing a response in the top three categories will be compared between treatments using chi-square tests by week. A Fisher's exact test will be used instead of a chi-square test when any cell in the contingency table has an expected count less than five.

Comfort related lens performance survey question results will be summarized using continuous summary statistics by treatment group and visit. Two-sided two-sample t-tests will be used to compare the treatment groups by visit.

The proportion of subjects with any slit lamp findings grade 2 or greater will be summarized categorically by treatment group and visit. Two-sided Fisher's exact tests will be used to compare the groups by visit.

Missing data will not be imputed.

There will be no adjustments for multiple comparisons.

There are no planned interim analyses.

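### The slit lamp safety endpoint is defined cumulatively in section 7.2, but section 7.6 summarizes and tests it only visit by visit, so the stated endpoint gets no comparison

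*Combined protocol and SAP*

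**What the plan says.** Section 7.2 (Study Endpoints) lists as the secondary safety endpoint: "The proportion of subjects with any slit lamp findings grade 2 or greater at any time". The unit is the subject and the time frame is cumulative.

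Section 7.6 (Statistical Analysis) gives the analysis: "The proportion of subjects with any slit lamp findings grade 2 or greater will be summarized categorically by treatment group and visit". The test follows the same layout: "Two-sided Fisher's exact tests will be used to compare the groups by visit".

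On population, section 7.5 states: "Analyses of safety data will include all dispensed subjects". Section 7.6 describes the safety set in terms of eyes: "for all dispensed eyes (completed and discontinued eyes pooled) for safety endpoints". It also states: "Missing data will not be imputed".

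Slit lamp examinations are not confined to the scheduled visits. Section 5.2.5.2 includes one at unscheduled visits and says: "Data from any additional visits within a scheduled visit interval will be captured on an Unscheduled Visit e-CRF". Section 5.2.8 provides for more after the study: "If a subject requires further follow-up upon discontinuation or completion of the study".

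**The concern.** The definition and the analysis describe different quantities. Section 7.2 asks what share of subjects ever had a grade 2 or worse finding. Section 7.6 asks what share had one at each visit. Followed as written, the plan reports the second and never the first.

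This does not look like loose drafting. The primary endpoint is defined for each of four weekly intervals in section 7.2 and tested week by week in section 7.6, so there the two sections agree. For safety, section 7.2 chose a cumulative definition and section 7.6 did not carry it through.

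Two things are at stake. First, the cumulative proportion cannot be recovered from the visit tables. Second, a finding seen only at an unscheduled visit clearly belongs to a cumulative endpoint, but section 7.6 does not say where it enters a by-visit table. If the cumulative comparison is added only after the data are seen, it is an unplanned analysis.

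**Working it through.** **1. The plan's own figure.** No rate, power or margin is given for this endpoint. The one power statement, in section 7.3, concerns proportions such as the primary ones: 0.500 v 0.670, 130 per group, two-sided 0.05. With pooled proportion 0.585:

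- null standard error = √(2 × 0.585 × 0.415 / 130) = 0.0611
- alternative standard error = √((0.25 + 0.2211) / 130) = 0.0602
- z = (0.17 − 1.96 × 0.0611) / 0.0602 = 0.83, so power is 0.798

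This matches the stated 80% but does not bear on the safety endpoint.

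**2. The texts side by side.**

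| Endpoint | Definition (7.2) | Analysis (7.6) | Match |
|---|---|---|---|
| Primary, take-home survey | each weekly interval | by week | yes |
| Safety, slit lamp grade 2+ | cumulative over the study | by visit | no |

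**3. What visit tables can and cannot show.** If an arm has a positive subjects at the first follow-up visit and b at the second, the number ever positive lies between max(a, b), when the smaller group sits wholly inside the larger, and a + b, when no subject is positive twice. The tables fix these bounds and nothing tighter.

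**4. Size, with assumed counts.** The documents give no grade 2+ rate. I assume 130 subjects per arm (section 7.3), all examined at both scheduled follow-up visits, and no unscheduled findings. All p-values are two-sided Fisher's exact; differences are in percentage points of 130.

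| Assumed visit counts | By-visit p | Ever-positive range | Cumulative p and difference |
|---|---|---|---|
| 2 v 8, then 2 v 8 | 0.103, 0.103 | 2–4 v 8–16 | 4 v 8: p=0.38, 4/130 = 3.1 points; 2 v 16: p=0.0009, 14/130 = 10.8 points |
| 1 v 8, then 5 v 5 | 0.036, 1.0 | 5–6 v 8–13 | from p=0.085 (5 v 13) to p=0.78 (6 v 8) |
| 1 v 3, then 1 v 3 | 0.62, 0.62 | 1–2 v 3–6 | from p=0.12 (1 v 6) to p=1.0 (2 v 3) |

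The extreme 2 v 16 needs complete overlap in one arm and none in the other. Less extreme overlaps for the first row give 2 v 8 (p=0.103) if the same subjects are positive at both visits in both arms, and 4 v 16 (p=0.009, 9.2 points) if different subjects are positive each time.

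The first row shows that two unremarkable visits can hide a cumulative difference. The second shows a by-visit result below 0.05 that no overlap carries over to the cumulative comparison. The third shows that with sparse findings the two approaches agree on significance whatever the overlap.

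**The case against.** The strongest reply is that little depends on this. The endpoint is secondary. Section 7.2 states hypotheses only for the take-home questionnaire and says that even the primary endpoints are not pass/fail criteria. No safety margin or success rule exists, so crossing 0.05 here triggers nothing. The by-visit analysis uses the same finding and test and bounds the cumulative count. The examinations are recorded, and serious and significant non-serious events are reported separately under section 6. Subjects with grade 2+ findings at entry are excluded, so counts may well be sparse.

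Most of this stands and limits the consequence. It does not remove the mismatch: bounds are not an estimate. Nor does adverse event reporting stand in for the endpoint, since section 6.2 lists corneal staining only from grade 3 and does not list limbal or bulbar injection by grade.

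A reader might infer that the construction rules are wholly open, including whether one eye suffices and whether unscheduled examinations count. The documents do not support that. A proportion of subjects with any finding naturally means a finding in either eye. Wear is bilateral, and section 3.3.3 discontinues the subject when the other eye is discontinued, so the reference to eyes in section 7.6 describes the same people. A cumulative definition likewise already takes in unscheduled examinations; what section 7.6 omits is where they enter its by-visit tables. The real ambiguity of scope is post-study follow-up.

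**Conclusion.** The point holds. As written, section 7.6 does not estimate the safety endpoint defined in section 7.2, and no readable section supplies the cumulative comparison. This is an analysis that does not match its endpoint, not merely a missing detail, and it should be corrected.

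The numerical size is unknown. Under the assumed counts the cumulative result may be stronger than, weaker than or equivalent to the by-visit results, depending on the overlap of subjects between visits. A reader might infer that the by-visit tests generally lose power, that a safety signal would be missed, or that a conclusion would change. None of these is shown: the counts are chosen for illustration, the documents give no rate, and no decision rests on the result. Nor is the underlying information lost, since it sits in the case report forms. I also describe this as the only readable safety endpoint, because a figure is missing from the text directly after the list.

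**What to change.** Add to section 7.6 one summary and one two-sided Fisher's exact test, by lens actually received, of the proportion of dispensed subjects with at least one grade 2 or greater finding in either eye at any slit lamp examination after dispensing and through study exit, whether scheduled or unscheduled.

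State whether post-study follow-up examinations (section 5.2.8) count. Report, per arm, the number of dispensed subjects with no examination after dispensing, so that the denominator is clear given that nothing is imputed. Keep the by-visit summaries and tests as supportive.

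The cost is one or two sentences and one table row. No new examination or data collection is needed.

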## **8.1 DATA QUALITY ASSURANCE**

### **8.2 Study Monitoring plan**

Bausch + Lomb representatives and or designees must be allowed to visit all study site locations to assess the data, quality, and study integrity in a manner consistent with applicable health authority regulations and the procedures adopted by Bausch + Lomb Clinical Affairs.

Prior to the start of the study, member(s) of Bausch + Lomb will review the protocol, e-CRFs, regulatory obligations, and other material or equipment relevant to the conduct of the study with the Investigator/Sub-Investigator and relevant study site personnel.

The Take Home Lens Performance Surveys do not relate to primary efficacy end points and will not be monitored.

Monitoring, online review and telephone consultations will occur as necessary, during the course of the investigation to verify the following:

- The rights and well-being of subjects are protected
- Completeness and accuracy of the forms
- The conduct of the investigation is in compliance with the currently approved protocol/amendment, 21CFR Parts 50, 54, 56 and 812, and 42 USC 282(j). The protocol was developed with consideration of the provision in: ISO 14155:2011 Clinical investigation of medical devices for human subjects – Good Clinical Practice; ISO 11980:2012 Ophthalmic Optics - Contact lenses and contact lens care products - Guidance for clinical investigations; ICH GCPs; and applicable local regulations.
- The integrity of the data, including adequate study documentation
- The facilities remain acceptable
- The Investigator and site personnel remains qualified and able to conduct the study
- Test article accountability

During the course of the study, if the Sponsor determines that an Investigator is not compliant with the protocol and/or applicable regulatory requirements, the Sponsor will take action to secure compliance. In addition, the Sponsor may terminate the

Investigator's participation in the study if appropriate, or if the Investigator remains non-compliant despite the Sponsor's actions.

### **8.3 Source Documentation**

All medical information obtained at each study visit must be recorded in the subject's record (source documentation) in real time as it is collected. Source documentation consists of original subject documents, as well as data and records with information relevant to the subject and his/her participation in the study. The data collected in the e-CRFs at all the study visits will be provided to the Investigator by the sponsor after the conclusion of the trial.

Examples of source documents include: hospital records, clinical and office charts, laboratory notes, memoranda, signed ICF, evaluation checklists, recorded data from automated instruments, copies or transcriptions certified after verification as being accurate copies, and information initially recorded in an electronic format.

Only subjects are to record information in the Take Home Lens Performance Surveys. **The Investigator or designees should review subject completed home surveys during study visits for completeness and accuracy.** If an entry is found to be illegible or a mistake is found (e.g., incorrect year was recorded), the subject should be instructed to edit the entry by drawing a single line through the original entry, entering the new information, and dating and initialing the change. If the survey(s) is not complete at the return visits the Investigator or designees should ensure it is completed prior to the subject's dismissal.

### **8.4 Case Report Forms and Data Verification**

Subject data required by this protocol are to be directly entered into the e-CRFs using single data entry with visual verification. The Investigator and his/her study site personnel will be responsible for completing the e-CRFs. The Investigator is required to verify that all of the requested information is accurately recorded on the e-CRFs. All information requested on the e-CRFs needs to be supplied, including subject identification and initials, date(s), assessment values, etc., and any omission or discrepancy will require explanation. Take Home Lens Performance Survey data will be collected and processed according to the policies and procedures of the CRO, and will not be included on e-CRFs or verified by Bausch + Lomb.

The study monitor will be responsible for reviewing and verifying the data recorded on the e-CRFs per the study Monitoring Plan. The Investigator and study site personnel will be responsible for answering all queries.

A copy of the e-CRFs for each subject will be provided to the Investigator at the conclusion of the study.

### **8.5 Recording of Data and Retention of Documents**

Subject data recorded on e-CRFs during the study will be documented in a coded fashion. The subject will only be identified by the subject number and by their initials if also required. Confidentiality of subject records must be maintained to ensure adherence to applicable local privacy regulations.

The Investigator must retain essential documents indefinitely after the completion of the study, unless otherwise notified by the Sponsor. The Investigator agrees to adhere to the document retention procedures when signing the protocol Investigator Statement of Approval.

Essential documents include but are not limited to the following:

- IRB/EC approvals for the study protocol, all amendments, ICF(s), and advertisements
- IRB/EC annual study review
- IRB/EC correspondence and reports (e.g., AE reports, protocol deviations, and safety updates)
- regulatory documents (e.g., Financial Disclosure and Delegation of Authority forms)
- e-CRFs (will be provided by the sponsor after the completion of the trial)
- subject's signed ICF
- Device Investigator Agreement
- accountability records for the test article(s)
- correspondence from and to the Sponsor
- any other documents relevant to the conduct of the study

In the event that study records are transferred to another location, the Investigator will provide notice of such transfer in writing to Bausch + Lomb Clinical Affairs.

#### **8.6 Auditing Procedures**

Audits of clinical research activities in accordance with the Sponsor's internal Standard Operating Procedures to evaluate compliance with the principles of GCP may take place. A regulatory authority may also wish to conduct an inspection (during the study or after its completion). If an inspection is requested by a regulatory authority and/or IRB/EC, the Investigator must inform the Sponsor immediately that this request has been made.

#### **8.7 Institutional Review Board**

The Investigator should ensure their participation in the study, in addition to the protocol, subject recruitment materials (written information or materials including web pages, radio advertisements, television spots or written text developed to encourage subject enrollment) and the ICF to be used in this study are approved by their institution IRB/EC, or if not using their institution's IRB, approved by the reviewing central IRB/EC prior to entering any subjects in the study. Documentation of IRB/EC approval of the study protocol and informed consent must be provided to the Sponsor prior to initiation of the study. In addition, the Investigator must ensure that the reviewing IRB/EC has provided approval for any protocol amendments prior to implementation. If the amendment necessitates a revision to the ICF, the Investigator should ensure the revised form is also submitted to and approved by the Sponsor and the IRB/EC and implemented as directed.

#### **8.8 Publication of Results**

All study data generated as a result of this study will be regarded as confidential, until appropriate analysis and review by the Sponsor or its designee and the Investigator(s) are completed. The results of the study may be published or presented by the Investigator(s) after the review by, and in consultation and agreement with the Sponsor, and such that confidential or proprietary information is not disclosed.

Study ROC2-17-014 - Protocol

Prior to publication or presentation, a copy of the final text should be forwarded by the Investigator(s) to the Sponsor or its designee, for comment. Such comments shall aim to ensure the scientific integrity of the proposed publications and/or presentations and ensure that the data and material referring to Bausch + Lomb products and activities receive fair, accurate, and reasonable presentation.

## **APPENDIX B: METHODS OF CLINICAL EVALUATION**

Any changes to the procedures described in this appendix will be provided under separate cover.

### **1.1 Visual Acuity/Refraction**

It is essential that a standard procedure be used to obtain VA measurements. The VA and refraction measurements should be obtained by a physician, optometrist, or trained technician. All VA/Refraction must be measured using a phoropter in 0.25 D steps. One standard logMAR, chart high 90% contrast, with Sloan letters will be used to obtain the VA measurements in this study. The following VA equipment from Precision Vision, Inc. will be used in this study: 90% High Contrast 6.5 feet (2.0 meters) testing distance Translucent Chart (CAT. NO. 2103-2), and the Precision Vision Small Illuminator Cabinet (CAT. NO. 914).

### **1.2 Illumination of the logMAR Chart and Room Illumination**

The internal illumination of the logMAR chart should be turned on. This will provide the nominal contrast for each of the charts. **Room illumination should be turned off**, to ensure that the illumination is consistent for each measurement. Ambient sources of light in the room, such as computer monitors, should be turned off or covered. A small source of illumination may be used to allow recording of data and to ensure that it is not difficult or dangerous for staff or subjects to move around the testing area, but these light sources should not be placed so that they are directed toward the subject during testing. The room lighting and any ambient sources should be consistent in their use and placement at each subject visit throughout the course of this study.

### **1.3 Determination of High Contrast Visual Acuity**

The subject should be seated so that the distance from the subject's eyes to the logMAR chart is 6.5 feet (2.0 meters). The chart should be at eye level for the subject. The logMAR charts have two alternative letter sequences from 28 letters (0.3 logMAR) to 62 letters (-0.3 logMAR). It is recommended that one letter sequence is used for the right eye, and the second letter sequence is used for the left eye, to minimize learning effects at each visit. Care should be taken to completely occlude the eye not being measured.

Since the test distance of the chart is not at optical infinity, refractive power compensation is required to simulate optical infinity. The VA should be measured through the phoropter using the distance refractive correction with the addition of +0.50 D to compensate for the reduced test distance of 6.5 feet (2.0 meters).

If all letters are correctly identified on any given line, then the subject is encouraged to read the next smaller line. When the subject says they cannot read a letter, they should be required to guess. A maximum effort should be made to identify each letter. The subject continues reading down the chart to the last letter of a given line, **until the subject has missed 3 letters on a line with 5 letters**. The incorrect letters can occur at the beginning, middle, or end of this line and do not have to be consecutive.

Study ROC2-17-014 - Protocol

The number of letters CORRECT will be recorded in the e-CRF. All correct letters will be entered into the system and the acuity score will be calculated during the analysis. To monitor the subjects' acuity during the trial, a Snellen – logMAR conversion table is provided below.

Snellen	logMAR
20/160	0.9
20/125	0.8
20/100	0.7
20/80	0.6
20/63	0.5
20/50	0.4
20/40	0.3
20/32	0.2
20/25	0.1
20/20	0
20/16	-0.1
20/12.5	-0.2
20/9.5	-0.3

